STUDY PROTOCOL COVER PAGE

Official Title: Randomised Controlled Trial of Two Different Cumulative Dosages of Roaccutane for Cystic Acne

Short Title: Roaccutane 120 mg/kg vs 150 mg/kg for Cystic Acne

Principal Investigator: [name], St George Hospital, Kogarah NSW, Australia

Study Identifier (NCT Number): To be assigned by ClinicalTrials.gov upon registration

Date: 23 June 2005

PROTOCOL

RANDOMISED CONTROLLED TRIAL OF TWO DIFFERENT CUMULATIVE DOSAGES OF ROACCUTANE FOR CYSTIC ACNE

Objective: Comparison of the effectiveness of Roaccutane at total cumulative dosages of 120 mg/kg vs 150 mg/kg.

Clinical Hypothesis: A 150 mg/kg cumulative dosage regimen is more effective at treating acne vulgaris and the presence of a remission from the disorder than 120 mg/kg.

Methodology: The study will be a multicenter, controlled, randomized study.

Number of subjects: It has been determined that to detect a 10% difference between the two dosage schedules of Roaccutane which are being tested (120mg/kg vs 150mg/kg) 450 subjects will be required with 225 in each group.

Diagnosis and Main Inclusion Criteria: Male or Female subjects, of any age, of any race, with a clinical diagnosis of nodulo-cystic acne as well as patients who have been unresponsive to standard acne vulgaris treatments.

Exclusion Criteria: pregnant or lactating female patients, female patients with polycystic ovarian syndrome, insulin resistance syndrome, previous use of Roaccutane, patients with congenital adrenal hyperplasia, patients with any internal malignancy (excluding skin cancer); females of reproductive potential who refuse to take the oral contraceptive pill to take roaccutane; patients who in the investigator's opinion would be unlikely to be compliant.

Investigational Product: Roaccutane 20mg tablets 150mg/kg total dose.

Comparator Product: Roaccutane 20mg tablets 120mg/kg total dose

Study Duration/Visits: Visits include before treatment initiation, and at least every two months thereafter, including when the 120mg/kg dose and at 150mg/kg cumulative doses are reached. The patients are assessed 3 months after finishing roaccutane and at one year after roaccutane treatment has ceased to record response and recurrence rates.

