Criteria for Evaluation: Acne lesion counts will consist of counting specifically white heads, blackheads, papules, pustules, nodules, deep pustules measured on both the left and right sides of the face, the same lesions will be measured on the chest and on the back. Scarring assessments will be done in terms of icepick scars, macular atrophic scars, follicular macular atrophic scars, hypertrophic/keloid scars and peri-follicular papular scars on the face, chest and back. An acne grade will also be assigned which ranges from 1 - 8. This acne grade has been established in the article "*Predictive*

factors for failure of isotretinoin treatment in acne patients; results from a cohort of 237 patients", Dermatology 1999;198: 278-283.

Other methods of note:

[figure not shown]
1. For consistency, all female patients of child bearing potential will be asked to use an oral contraceptive pill. A second form of contraception will be required.
2. Standard investigations for this study to identify potential factors include two negative serum pregnancy tests immediately before starting on treatment, testosterone level, sex hormone binding globulin, luteinizing hormone level, follicle stimulating hormone level, androstenedione level, 17 hydroxy-progesterone level and glucose tolerance tests. Transabdominal and/or transvaginal ovarian ultrasound when appropriate.
3. Other laboratory tests will be drawn before starting roaccutane including a full blood count, UEC, lipid panel, and liver function tests.
4. Once the decision to start Roaccutane has been taken, patients will be randomised to either treatment group that being 120mg/kg or 150mg/kg cumulative dose. If the patient's acne is still active during the month they are due to cease treatment their course of treatment will be continued.
5. Before commencing on either Roaccutane dose a study consent form, which has been approved by the SESIAHS Ethics Committee,
6. Separate forms are available for minors.

NAME OF THE DRUG

ROACCUTANE

(isotretinoin)

CAS 4759-48-2

13-cis-Retinoic Acid

Chemically, isotretinoin is (2Z, 4E, 6E, 8E)-3,7-dimethyl-9-(2,6,6-trimethylcyclohex-1-enyl)nona-2,4,6,8-tetraenoic acid and is also known as 13-cis-retinoic acid. Isotretinoin is related to both retinoic acid and retinol (vitamin A). The molecular formula is C₂₀H₂₈O₂. Isotretinoin has a molecular weight of 300.44.

DESCRIPTION

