The major identified metabolite in blood and urine is 4-oxo-isotretinoin. Tretinoin and 4-oxo-tretinoin were also observed. After two 40 mg capsules of isotretinoin, maximum concentrations of the metabolite of 87 to 399 nanogram/mL occurred at 6 to 20 hours. The blood concentration of the major metabolite generally exceeded that of isotretinoin after 6 hours.

The mean \pm SD minimum steady-state blood concentrations of isotretinoin were 160 \pm 19 nanogram/mL in 10 patients receiving 40 mg twice daily. After single and multiple doses, the mean ratio of areas under the curves of isotretinoin to 4-oxo-isotretinoin is 3 to 3.5.

Excretion

The terminal elimination half-life of isotretinoin ranged from 10 to 20 hours in volunteers and patients. Following an 80 mg liquid suspension oral dose of ^{14}C -isotretinoin, ^{14}C -activity in blood declined with a half-life of 90 hours. Relatively equal amounts of radioactivity were recovered in the urine and faeces with 65-83% of the dose recovered. The apparent half-life for elimination of the 4-oxo-metabolite ranged from 11 to 50 hours with a mean of 29 hours. This metabolite is subject to recycling in the enterohepatic circulation.

INDICATIONS

ROACCUTANE is indicated for the treatment of severe cystic acne, and a single course of therapy has been shown to result in complete and prolonged remission of disease in many patients. If a second course of therapy is needed, it should not be initiated until at least eight weeks after completion of the first course, since experience has shown that patients may continue to improve while off drug. Because of significant adverse effects associated with its use, ROACCUTANE should be reserved for patients with severe cystic acne who are unresponsive to conventional therapy, including systemic antibiotics.

CONTRAINdications

Use in Pregnancy (Category X): ROACCUTANE must not be used by females who are pregnant or who may possibly become pregnant while undergoing treatment.

Major human fetal abnormalities related to ROACCUTANE administration have been reported, including hydrocephalus, microcephalus, abnormalities of the external ear (micropinna, small or absent external auditory canals), eye abnormalities (including microphthalmia), cardiovascular abnormalities, facial dysmorphia, cleft palate, thymus gland abnormality, parathyroid gland abnormalities and cerebellar malformation.

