All patients initially should receive ROACCUTANE at doses up to 0.5 mg/kg/day bodyweight daily for a period of two to four weeks, when their responsiveness to the drug will usually be apparent. It should be noted that transient exacerbation of acne is occasionally seen during this initial period. Satisfactory initial responses have been reported from 0.05 mg/kg/day. Relapse rates on the lower doses are higher (a second course may be required in about two-thirds of patients on 0.1 mg/kg/day for 16 weeks), but there is decreased incidence and severity of adverse reactions at lower doses.

The daily dosage should be taken with food in the nearest number of whole capsules, either as a single dose or in two divided doses during the day, whichever is more convenient.

Doses up to 1 mg/kg/day may be used in patients refractory to initial treatment at lower doses.

The above daily dosages of ROACCUTANE should be continued for 16 weeks to complete the course of treatment.

After a period of two months off therapy, and if warranted by persistent severe cystic acne, a second course of therapy may be initiated.

OVERDOSAGE

Clinically, overdose has been associated with transient headache, vomiting, facial flushing, cheilosis, abdominal pain, headache, dizziness and ataxia. All symptoms quickly resolved without apparent residual effects.

The oral LD₅₀ of ROACCUTANE is greater than 4000 mg/kg in rats and mice and approximately 1960 mg/kg in rabbits.

PRESENTATION

Soft gelatin capsules

10 mg x 60 capsules, reddish-violet in colour, oval shaped, imprinted with ROA 10.

20 mg x 60 capsules, reddish-violet in colour one half, white opaque the other half, oval shaped, imprinted with ROA 20.

SPONSOR

Roche Products Pty. Limited

[name]

[name]

TGA Approved: 18 January 2001

Date of most recent amendment: 23 June 2005

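### Does a possible second course of isotretinoin leave the 3-month and one-year recurrence visits without a fixed starting point?

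*Protocol*

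**What the plan says.** The follow-up schedule is one sentence under Study Duration/Visits: "The patients are assessed 3 months after finishing roaccutane and at one year after roaccutane treatment has ceased to record response and recurrence rates".

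The trial's own text on when treatment ends is in Other methods of note, item 4. At the start of treatment, "patients will be randomised to either treatment group that being 120mg/kg or 150mg/kg cumulative dose". The same item adds: "If the patient's acne is still active during the month they are due to cease treatment their course of treatment will be continued". The Objective, the two product descriptions and the visit schedule are also written in terms of the cumulative totals.

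The manufacturer's product information is reproduced after the trial section. Its Dosage and Administration section says: "The above daily dosages of ROACCUTANE should be continued for 16 weeks to complete the course of treatment". It gives a starting dose of up to 0.5 mg/kg/day for two to four weeks, and then: "Doses up to 1 mg/kg/day may be used in patients refractory to initial treatment at lower doses". On re-treatment it says: "After a period of two months off therapy, and if warranted by persistent severe cystic acne, a second course of therapy may be initiated". The Indications section says of a second course that "it should not be initiated until at least eight weeks after completion of the first course".

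The trial section does not mention a second course. Its exclusion for earlier use of the drug is an entry criterion and does not cover follow-up.

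**The concern.** Remission is part of the clinical hypothesis, so the two off-treatment visits carry much of the comparison. The document seems to offer three ends of treatment: the assigned total, a later date if acne is still active, and 16 weeks. If the 16-week text governed, neither arm could reach its total in one course, and a second course would be assigned treatment rather than re-treatment.

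A second course also creates two stop dates. Counted from the first, the one-year visit is not a year off drug. Counted from the second, it falls about a year and a half after the first stop. If re-treated patients were then scored only on their lesions at one year, some relapses would be missed, with more absolute points lost in the arm that relapses more.

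**Working it through.** The protocol gives no figure for this point, so there is none to reproduce. The checks use the document's own doses and intervals, with 16 weeks = 112 days, two months ≈ 61 days, three months ≈ 91 days and one year = 365 days.

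**1. Does a 16-week course reach the assigned totals?** Cumulative dose = daily dose × days.

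| Pattern over 112 days | Calculation | mg/kg |
|---|---|---|
| 0.5 mg/kg/day throughout | 0.5 × 112 | 56 |
| 4 weeks at 0.5, then 1 | 28 × 0.5 + 84 × 1 | 98 |
| 2 weeks at 0.5, then 1 | 14 × 0.5 + 98 × 1 | 105 |
| 1 mg/kg/day throughout | 1 × 112 | 112 |

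None reaches 120. The totals need 120/112 = 1.07 and 150/112 = 1.34 mg/kg/day over 16 weeks. Conversely, 120 mg/kg takes 120 days at 1 mg/kg/day and 240 days at 0.5; 150 mg/kg takes 150 and 300 days. The label's course length and the trial's totals therefore cannot both be met at the label's doses. The two texts differ by 120 − 112 = 8 to 300 − 112 = 188 days.

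**2. Does that make the visit dates ambiguous?** Let D be the day of the last dose. The visits fall at D + 91 and D + 365. The assigned total, the item 4 continuation and a 16-week stop each change the value of D. None changes the rule for counting from it. With one course, D is a single observed date and the patient has had 365 days off drug at the one-year visit under any of the three. The difference in step 1 affects when treatment stops, not how follow-up is counted.

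**3. What would a second course do?** Assume the earliest start the label allows and a further 112 days. Days are counted from the first stop.

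| | Start at 8 weeks | Start at two months |
|---|---|---|
| Second course starts | 56 | 61 |
| Days on drug at 3-month visit | 91 − 56 = 35 | 91 − 61 = 30 |
| Second course ends | 56 + 112 = 168 | 61 + 112 = 173 |
| Days off drug at one year | 365 − 168 = 197 | 365 − 173 = 192 |
| One-year visit if the clock restarts | 168 + 365 = 533 | 173 + 365 = 538 |

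The effect on an individual patient is real. These are earliest-start figures, and a later restart moves all of them.

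**4. How large could the bias be?** Suppose a share *s* of relapsing patients, equal in both arms, is re-treated and then scored as clear at one year. The observed difference in recurrence is the true difference × (1 − *s*). Taking the planned 10% difference as 10 percentage points, that is 10 × (1 − *s*): 10 points at *s* = 0 and none at *s* = 1. The document gives no value for *s*, and no passage says that a re-treated patient counts as clear. The one figure on second courses does not help: "a second course may be required in about two-thirds of patients on 0.1 mg/kg/day for 16 weeks" refers to 0.1 × 112 = 11.2 mg/kg, less than a tenth of the lower assigned total.

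**The case for a change.** The strongest case for a change is that the label stands inside the protocol and is the document's only source of a daily dose and of a course length in weeks, and that nothing says the trial section overrides it. Scoring can be left to a statistical analysis plan, but visit timing and the recording of re-treatment cannot: a visit held on the wrong date, or a restart date never collected, is lost. The remedy would be a few sentences and one date field.

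Part of this stands. The label's course length and the trial's cumulative totals do differ, and those passages must be reconciled as a matter of clinical management; this review does not say which is right. It is also true that the protocol gives no rule for a restart during follow-up.

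The rest does not carry the point. The trial section is consistent in describing treatment by total dose, while the 16-week and second-course text is general product information. The claim that restart dates would be lost assumes they go unrecorded, and the data-collection forms are not shown. The early-restart scenario is also narrow: item 4 continues treatment when acne is still active near the planned stop, so much persistent disease is dealt with before any drug-free interval begins.

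**Conclusion.** No change to the plan follows. For a patient with one course the starting point of follow-up is the last dose, and the one-year visit comes after 365 days off drug whichever rule led to the stop. The unanswered question concerns only patients who restart isotretinoin before one year: which stop date counts, and whether the restart is itself a recurrence. That is a gap analysts fill routinely, usually by counting from the end of the randomised course and fixing the status of a restart before the data are examined. No rule stated in the protocol is shown to give a wrong result.

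For one re-treated patient the effect could be 30 to 35 days on drug at the 3-month visit and 192 to 197 rather than 365 days off drug at one year. Those figures assume the earliest permitted start and a 16-week second course. The number of such patients, the bias and any loss of power cannot be derived from the document. The conclusion rests on reading the end of treatment as the actual last dose, and on the analysis plan or case report form covering restarts, as they commonly do.

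### Should patients be randomised at the 120 mg/kg visit instead of at treatment start, because the arms appear to differ only after 120 mg/kg?

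*Protocol*

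**What the plan says.** Item 4 under Other methods of note in the Protocol fixes the time of allocation: "Once the decision to start Roaccutane has been taken, patients will be randomised to either treatment group that being 120mg/kg or 150mg/kg cumulative dose".

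The two arms are given as "Roaccutane 20mg tablets 150mg/kg total dose" (Investigational Product) and "Roaccutane 20mg tablets 120mg/kg total dose" (Comparator Product). No daily dose is given separately for each arm.

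Visits (Study Duration/Visits) take place before treatment and "at least every two months thereafter, including when the 120mg/kg dose and at 150mg/kg cumulative doses are reached". The sample size of 450, 225 per group, is set "to detect a 10% difference between the two dosage schedules of Roaccutane which are being tested" (Number of subjects). Methodology says "The study will be a multicenter, controlled, randomized study" and does not mention masking.

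Item 4 also states that where a patient's "acne is still active during the month they are due to cease treatment their course of treatment will be continued". This applies to both arms.

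The Objective and Clinical Hypothesis compare effectiveness and remission between the two cumulative-dose regimens. Neither restricts the comparison to patients who get as far as 120 mg/kg.

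**The concern.** If both arms take the same daily dose, their assigned treatments are identical until 120 mg/kg. A patient who stops before that point is counted in an arm without having received anything that distinguishes it from the other. Such patients pull the two rates together and cost power. They cannot safely be removed afterwards, because no masking is described and knowing the target might affect who persists.

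A visit at 120 mg/kg is already scheduled, so allocating there looks like an inexpensive way to avoid both problems. At stake would be the power of a trial sized for a 10% difference.

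**Working it through.** **1. The plan's own figure.** Alpha, power and base rate are not given, so 225 per group cannot be re-derived from the protocol alone. It is attainable. With two-sided 0.05 and 80% power (both assumed), the requirement is 221 per arm for 78% vs 88% and 231 for 77% vs 87%. For 80% vs 90% with a 10% dropout inflation it is 222. The text therefore does not show whether 450 already contains an allowance for attrition.

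**2. Inputs for the comparison.**
- From the protocol: 225 per arm; a difference of 10%, read as percentage points.
- Assumed: two-sided 0.05; recurrence of 20% vs 10% or 30% vs 20%; equal dosing up to 120 mg/kg; a share k of starters reaching 120 mg/kg; early stoppers recurring at rate s in both arms, with s equal to the lower or the higher arm rate.

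**3. Formula.** Power = Φ[(Δ − 1.96·SE0)/SE1], where SE0 = √(2p̄(1−p̄)/n), SE1 = √((p1(1−p1)+p2(1−p2))/n) and p̄ is the mean of the two rates.
- Allocation at start: n = 225 and each arm's rate is k·p + (1−k)·s, so Δ = 10k points.
- Allocation at 120 mg/kg, same 450 starters: n = 225k and Δ = 10 points.

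**4. Worked case, 20% vs 10%.**
- No early stopping: SE0 = 0.03367, SE1 = 0.03333, z = (0.10 − 0.06598)/0.03333 = 1.02, power 84.6%.
- k = 0.85, s = 10%, at start: rates 18.5% and 10%, SE0 = 0.03296, SE1 = 0.03271, z = (0.085 − 0.06459)/0.03271 = 0.62, power 73.4%.
- k = 0.85, late: n = 191.25, SE0 = 0.03651, SE1 = 0.03616, z = (0.10 − 0.07157)/0.03616 = 0.79, power 78.4%.

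**5. All cases** (gains taken from unrounded powers):

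| Recurrence | k | At start | At 120 mg/kg | Gain (points) |
|---|---|---|---|---|
| 20 vs 10% | 0.95 | 80.2–81.3% | 82.8% | 1.4–2.5 |
| 20 vs 10% | 0.85 | 69.8–73.4% | 78.4% | 5.1–8.6 |
| 20 vs 10% | 0.70 | 51.6–58.5% | 70.2% | 11.7–18.6 |
| 30 vs 20% | 0.95 | 64.1–64.7% | 66.7% | 2.0–2.5 |
| 30 vs 20% | 0.85 | 54.1–55.7% | 61.8% | 6.1–7.7 |
| 30 vs 20% | 0.70 | 39.0–41.7% | 53.6% | 11.9–14.6 |

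With no early stopping the powers are 84.6% and 68.9%. At k = 0.85 late allocation wins back 45–58% of the loss. The reason is simple: allocation at start scales the signal by k, while late allocation scales it by √k.

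**6. The other reading of the 10%.** The sample-size sentence can equally mean the difference between the groups as randomised. Dilution is then already inside the 10 points, and allocation at start keeps the full 84.6% and 68.9%. Late allocation would exceed these (at k = 0.85, 88.6–91.4% and 74.9–76.9%), but there is no shortfall against the plan to repair.

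**7. What waiting costs.**
- From 450 starters, 450k patients are allocated: about 428, 383 or 315 at k = 0.95, 0.85, 0.70. All are below the stated 2 × 225.
- Keeping 450 allocated needs 450/k starters: about 474, 530 or 643.
- The result applies only to patients who reach 120 mg/kg, and some may decline allocation at that visit.

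**8. Interaction with the continuation rule.** Suppose 20% of patients at the visit are continued and show no contrast between arms (both at the lower rate; k = 0.85, 20 vs 10%, s = 10%). Power is then 56.3% at start and 61.7% late. Continuation costs 73.4 − 56.3 = 17.1 points with allocation at start and 78.4 − 61.7 = 16.7 with late allocation, against a gain of 61.7 − 56.3 = 5.4 from waiting. The rule also turns on the month in which treatment is due to end, which is not known until the arm is known. Later allocation could not be adopted until item 4 is reconciled with the assigned totals.

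**The case for a change.** The strongest argument for waiting is that only patients who reach 120 mg/kg can show what the extra 30 mg/kg does. The direction of the gain is the same in every case computed. Early stopping is foreseeable, since the attached product information lists several reasons for discontinuation. The range above is also not the widest possible. If early stoppers recur at 40–60% (an assumption), the 20 vs 10% case at k = 0.85 gives 63.8% to 59.0% at start against 78.4% late, a gain of about 15 to 19 points. At k = 0.95 it gives 78.2% to 76.2% against 82.8%, a gain of about 5 to 7.

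All of that stands as arithmetic. It does not show that the protocol has chosen wrongly:
- Equal dosing up to 120 mg/kg is an inference. The protocol speaks of two dosage schedules, and the product information under Dosage and Administration calls for individual adjustment. If daily dosing differs by arm, the proposal does not apply.
- Nothing in the protocol indicates a stopping share of 15% or more, and investigators are to exclude patients they expect not to comply.
- The risk that a known target changes persistence before 120 mg/kg is conjecture. In a comparison of everyone as randomised, it would be part of the effect of assigning that regimen and would not break the randomisation.
- How early stoppers are handled and which analysis set is used are commonly left to a statistical analysis plan, which is not at hand.

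**Conclusion.** The concern does not hold. Randomising at the decision to treat is valid and matches an objective framed as a comparison of regimens among those who start. Later allocation answers a narrower question, about patients who reach 120 mg/kg.

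With the same 450 starters and stoppers recurring at one of the arm rates, its advantage is 1.4 to 2.5 power points at 5% early stopping and 5 to 9 at 15%; it is larger if stoppers do much worse. All of this requires equal dosing up to 120 mg/kg. If the 10% is the difference as randomised, the planned power is intact. Against the gain stand a changed population, possible refusals, fewer than 225 per group unless more patients start, and a dependence on first reconciling the continuation rule.

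Statisticians could reasonably choose either design. That the daily dose per arm is not stated is missing detail and does not make the time of allocation an error.

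### Continuing treatment past the assigned dose in patients with active acne makes the 3-month response a comparison of strategies, not of the fixed 120 and 150 mg/kg doses in the Objective

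*Protocol*

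**What the plan says.** The Objective in the Protocol is a "Comparison of the effectiveness of Roaccutane at total cumulative dosages of 120 mg/kg vs 150 mg/kg". The product lines repeat the contrast as totals: "Investigational Product: Roaccutane 20mg tablets 150mg/kg total dose" and "Comparator Product: Roaccutane 20mg tablets 120mg/kg total dose". The sample size of 450, with 225 per group, is meant "to detect a 10% difference between the two dosage schedules of Roaccutane which are being tested".

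Item 4 of Other methods of note randomises patients to one of the two cumulative doses and then adds: "If the patient's acne is still active during the month they are due to cease treatment their course of treatment will be continued". The wording is the same for both arms. The readable text ties the state of being active to no grade or count. It also sets no maximum extra dose, total dose or duration.

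Study Duration/Visits schedules visits "at least every two months thereafter, including when the 120mg/kg dose and at 150mg/kg cumulative doses are reached". It attaches the outcome rates to later dates: "The patients are assessed 3 months after finishing roaccutane and at one year after roaccutane treatment has ceased to record response and recurrence rates". Lesion counts and a grade ("An acne grade will also be assigned which ranges from 1 - 8") are provided under Criteria for Evaluation, but that section does not say at which visits they are taken and does not link them to item 4.

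**The concern.** For a continued patient the total dose is no longer 120 or 150 mg/kg. It is the assigned dose plus an amount given because the assigned dose had not yet worked. Both the 3-month and the one-year assessments are timed from the actual end of treatment, so the extra drug comes before the response that is recorded.

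Continuation is thus triggered by outcome, in the very patients in whom a difference in response between the doses would show. At stake is what the trial's response result means: the effect of stopping at 120 rather than 150 mg/kg, or the effect of planning to stop there and continuing where needed. The Objective and product lines point to the first. Item 4, combined with the visit schedule, delivers the second. An analysis plan written later can choose how continued patients are handled, but it cannot give them a common trigger or limit once they have been treated.

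**Working it through.** **Stated figure.** 2 × 225 = 450. The Protocol gives no alpha, power, base rate or endpoint for the 10% difference, so 225 cannot be reproduced from its own inputs. It can be approached under assumed ones: two-sided 5% and 80% power need 221 per arm for 12% vs 22%, and 231 per arm for 13% vs 23%. The figure is not shown to be wrong, and the point does not rest on it.

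**Gap between the arms.** 150 − 120 = 30 mg/kg. The trial fixes no daily dose. Dosage and Administration, in the product information included in the Protocol, gives starting doses up to 0.5 mg/kg/day and up to 1 mg/kg/day in refractory patients.
- 30 / 1.0 = 30 days
- 30 / 0.5 = 60 days

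So 30 to 60 days of continuation at these doses takes a 120 mg/kg patient to the other arm's total.

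**Does anything else cap the extension?** The only duration given is the 16-week course in Dosage and Administration. 16 × 7 = 112 days, and 112 × 1 mg/kg/day = 112 mg/kg. That is below both assigned doses, so it cannot serve as a limit on item 4.

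**Order of events.**
- Not continued: visit at the assigned dose, stop, response at 3 months. Dose behind the response: 120 or 150.
- Continued: visit at the assigned dose, acne active, extra dose *e*, stop, response at 3 months. Dose behind the response: 120 + *e* or 150 + *e*, with *e* unlimited in the readable text.

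The visit at the assigned dose precedes any extension, but the Protocol does not name it as the source of the response rate.

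**Mean dose contrast.** If shares q120 and q150 are continued by *e* mg/kg, the contrast is (150 + q150·e) − (120 + q120·e) = 30 − (q120 − q150)·e. The shares are not in the document. With *e* = 30 and assumed shares:
- 10% and 10%: 30 − 0 = 30 mg/kg
- 22% and 12%: 30 − 0.10 × 30 = 27 mg/kg
- 50% and 30%: 30 − 0.20 × 30 = 24 mg/kg

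On these assumptions the arms stay well apart on average. The difficulty lies in who receives the extra dose.

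**Can the effect on response be derived?** Let p be the share active at the assigned dose, d the fraction of them who would clear after stopping, and c the fraction who clear when continued. Non-response is p(1 − d) without continuation and p(1 − c) with it. The Protocol gives none of p, c or d. Purely to show how open the answer is, take p = 22% (120 arm) and 12% (150 arm):
- No continuation, d = 0: 22 − 12 = 10 points
- No continuation, d = 0.5: 11 − 6 = 5 points
- Continuation, c = 0.5 in both arms: 11 − 6 = 5 points
- Continuation, c = 0.25 (120 arm) and 0.5 (150 arm): 16.5 − 6 = 10.5 points
- Continuation, c = 0.5 (120 arm) and 0.25 (150 arm): 11 − 9 = 2 points

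Depending on the assumed rates, the difference shrinks, is unchanged or grows. Neither its size nor its direction follows from the document.

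**The case against.** **It is a sound comparison of strategies.** The hypothesis speaks of a regimen and the sample-size sentence of dosage schedules. The rule is worded identically for both arms, and comparing two planned stopping doses under a common continuation rule is legitimate in a randomised trial. This stands: nothing in item 4 invalidates the randomised comparison. But the Objective and both product lines name totals, and the Protocol never says that a strategy comparison is intended.

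**Assessments before continuation are already planned.** The visits at 120 and 150 mg/kg come before any extension, and the grade and counts are collected in the trial. This also largely stands. The assigned-dose contrast is recoverable and the remedy is cheap. What remains is that response rates are attached to the post-treatment assessments.

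**Continuation is good care, and an analysis plan can deal with it.** Dosage and Administration says that response varies and that dosage needs individual adjustment, so the rule is reasonable and should be kept. How continued patients are analysed may be left to the analysis plan. The treatment rule and its limit belong in the Protocol.

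**No criterion for active acne.** On its own this is only missing detail. A figure under the same heading could not be read, so the absence of a criterion or limit is certain only for the readable text.

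**A stronger reading to resist.** A reader might infer that item 4 costs the trial power. The documents do not support that. With 225 per arm, two-sided 5% and the assumed 22% vs 12%, continuation with half clearing in both arms gives 48% power. Without continuation, power would be 81%, 67% or 48% as 0, 25% or 50% clear off drug. The loss could therefore be 33, 19 or 0 percentage points. Unequal clearing gives 94% (the 10.5-point case) or 11% (the 2-point case). Every rate is assumed, Indications says that patients may go on improving after stopping, and the endpoint behind the 10% is not stated. These figures are not evidence of harm.

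**Conclusion.** The point holds in a limited form. The Protocol names a contrast of fixed total doses, continues treatment beyond them because of outcome without a limit in the readable text, and takes response rates only after treatment has actually ended. The 3-month response therefore compares planned stopping doses plus continuation. The one-year recurrence rate, also timed from actual cessation, carries the same label.

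The size that can be stated is the dose gap: 30 mg/kg, or 30 to 60 days at 1 to 0.5 mg/kg/day. This uses the product-information doses, because the trial fixes none. The effect on the difference or on power cannot be sized or signed. It should not be inferred that the trial is invalid or underpowered, or that the two arms end at the same dose. The mismatch should be corrected because it decides which question the response result answers.

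**What to change.** Amend item 4 and Study Duration/Visits as follows.

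- **Response at the assigned dose.** Record grade and lesion counts at the already scheduled visit when the assigned 120 or 150 mg/kg is reached, before any continuation, and name this as the result for the assigned dose.
- **One rule for continuation.** Use a single grade or lesion-count trigger and a single maximum extra dose or duration, the same in both arms, and record the cumulative mg/kg actually taken. The values are a clinical choice; the document offers none.
- **Label the later outcomes.** Keep patients in their randomised arm and describe the 3-month and one-year results as a comparison of strategies that include continuation.

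The cost is about one paragraph and no extra visits, since the visits and the measures are already in the Protocol. There are two downsides. A reading at the dose visit misses later improvement off drug, which is why the post-treatment outcomes should stay. A fixed trigger and cap also slightly narrow clinical discretion over who is continued and for how long.
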